9.2 Laboratory Values Beyond the Limits of Quantification

Laboratory values of the form of “ $< x$ ” (i.e., below the lower limit of quantification) or “ $> x$ ” (i.e., above the upper limit of quantification) will be imputed as “ x ” for the purpose of calculating summary statistics and comparing to normal ranges. These values will remain as “ $< x$ ” or “ $> x$ ” in the listings.

9.3 Important Protocol Deviations

Potential planned or unplanned protocol deviations noted during clinical monitoring will be documented by category (i.e., inclusion criteria, exclusion criteria, study drug, safety assessment, efficacy assessment, visit window, informed consent, prohibited medication, and other). All deviations will be reviewed, categorized, designated important or not important, and finalized prior to database lock. Important protocol deviations will be defined as those potentially impacting safety or efficacy assessments. Additional details of what will be considered important can be found in the Protocol Deviation Guidance document.

10.0 Interim Analyses

There are no formal interim analyses in the study. Tumor responses will be reviewed for the CAE population to make decisions per the Predictive Probability Design on whether a cohort should be stopped for lack of tumor response as detailed in Section 6.2.

11.0 Planned Analysis

PK sub-study patients will be excluded from any main study summaries and will be presented in PK sub-study specific summaries only. Screen Failures will be summarized in a Screen Failure table, but otherwise excluded from all tables and listings. Listings will include all relevant derived variables.

All data collected during this study will be displayed in data listings, unless otherwise specified. Data listings will be presented separately for enrolled patients in the main study and those in the PK sub-studies.

Descriptive statistics (mean, median, standard deviations [STD] or standard error, first quartile [Q1], third quartile [Q3], minimum and maximum values) for continuous variables will be presented. Mean and median will be presented to 1 decimal more than original data. STD will be presented to 2 decimals more than original data. Minimum and maximum values will match the decimal points in the original data. For categorical variables, summary measures will include the frequency and percentage (with 1 decimal place) of patients in each category.

Safety summaries will be presented for assessments on-treatment (as defined in Section 8.4) and will include patients from both the safety lead-in and phase 2 parts of the study. Efficacy summaries will be presented for assessments on-study (defined in Section 8.2) and will include patients receiving the recommended phase 2 dose (120mg QD) only. All tables will be presented by treatment arm and strata.

Unless otherwise noted, missing data will not be imputed or carried forward.

All data summaries and tabulations will be prepared with SAS® v9.4 or higher.

11.1 Analysis for Main Study (non PK sub-studies)

11.1.1 Patient Disposition

The number and percentage of patients in each analysis population will be presented, along with the patients who withdrew from the study, discontinued Nivolumab or the investigational study drug, with the breakdown of corresponding withdrawal/discontinuation reasons. The number and percentage of deaths, including cause of death and the duration on treatment (time from first dose date to end of treatment, in months) will also be presented.

The number of patients enrolled by site and overall will be presented.

Disposition will be summarized descriptively by treatment arm and strata.

11.1.2 Important Protocol Deviations

Important protocol deviations (see definition in Section 9.3) for patients in the Enrolled Population will be listed only. A listing of patients who enroll with inclusion or exclusion criteria exceptions will also be provided.

11.1.3 Demographic and Baseline Characteristics

Demographic and baseline data will be summarized descriptively using the Safety population.

Demographic variables to be summarized include sex, reproductive status for female, race, ethnicity, age (years), baseline weight (kg), baseline height (m), baseline Eastern Cooperative Oncology Group (ECOG) status, and smoking history.

Primary disease history will summarize Histology (Adenocarcinoma, Large Cell Carcinoma, and Other), Current Stage (Locally Advanced, Metastatic), the time since diagnosis and the time since metastatic diagnosis.

Prior primary disease treatment (systemic therapies including platinum therapies and checkpoint inhibitors, radiotherapy, and surgery) will summarize the following:

- Prior Systemic Therapy - Platinum Agent Received (Cisplatin, Carboplatin, Other)
- Prior Checkpoint Inhibitor - (Nivolumab, Pembrolizumab, Durvalumab, Atezolizumab, Avelumab, Other)
- Best Response to Prior Checkpoint Inhibitor
- Prior Regimens (Number of Regimens and Type)
- Prior Radiotherapy - Type (Adjuvant, Palliative)
- Prior Surgery - Location (Lung, Liver, Lymph Node, Adrenal, Brain, Other)

Demographic, primary disease history, and prior primary disease treatment data will also be listed by patient.

11.1.4 Prior and Concomitant Medications and Procedures

Concomitant medications will be coded using World Health Organization (WHO) Drug Enhanced (Version: March 2016).

Prior and concomitant medications will be tabulated separately for the Safety Population by Anatomical Therapeutic Chemical (ATC) Classification (2nd Level) and preferred drug name using counts and percentages. The number and percentage of patients using at least one medication will be summarized.

Prior and concomitant medications along with concomitant procedures will be listed.

11.1.5 Medical History

Medical history will be tabulated using the Safety Population by system organ class (SOC) and preferred term (PT). Medical history will also be listed by patient.

Signs and symptoms of the patient's cancer diagnosis and/or comorbidities present prior to Day 1 of study treatment dosing are recorded in the CRF as medical history.

11.1.6 Efficacy Analyses

All efficacy analyses will be presented by planned treatment arm and strata, as described in Section 8.5.

The 120mg dose of Sitravatinib was given to patients in both the lead-in phase and in phase 2, hence the efficacy results will be presented for all subjects receiving this dose combined across phases.

If a treatment arm includes patients only in the lead-in phase and not in phase 2, then only listings will be presented for this treatment arm. If a treatment arm was not initiated, then no efficacy results will be presented.

11.1.6.1 Primary Variable

Descriptive statistics for ORR and BOR (CR, PR, SD, PD and NE) based on the response assessments by the Investigator will be presented by treatment arm and strata. Exact 95% Clopper-Pearson CIs for ORR will also be presented.

An exact test for single proportion (one-sided $\alpha=0.025$) will be performed to test H_0 : ORR $\leq 5\%$ against H_1 : ORR $> 5\%$ for CIT-experienced and PD-L1 no/low or CIT naïve for each treatment arm which proceeds to Phase 2 and test H_0 : ORR $\leq 27\%$ against H_1 : ORR $> 27\%$ for PD-L1 high of CIT naïve.

Patients who cannot be assessed for response will be counted as non-responders.

The primary analysis will be conducted using the FAS with supportive analyses presented using the CAE population.

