Disease response and progression as documented by the Investigator in the CRF will be the basis for patient management and study expansion decision making. Unconfirmed objective responses recorded in the CRF may be used as the initial basis for expansion of study enrollment; however, follow-up evaluations on patients with unconfirmed responses must continue to support the decision to continue to the full number of patients to be included in the next stage. Disease assessments will be performed until objective disease progression is documented or subsequent anti-cancer therapy is begun. Central radiology review for disease response and progression may be added to the study during Stage 2. If this occurs, central review of all radiologic assessments performed in the study will be conducted (including retrospective review of patients enrolled in Stage 1), and central radiology review for disease response will be the basis for the primary statistical analyses to estimate the objective response rate and its confidence interval (CI), as well as the DoR and PFS.

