6.2.1.2 Phase 2 CIT-experienced and CIT-naïve with no/low PD-L1 expression

This Phase 2 study will use a Predictive Probability Design (Lee 2008) in each treatment arm and strata. In creating the statistical designs, the Type 1 error (α) is constrained to <0.05 and power ($1-\beta$) is constrained to ≥ 0.90 .

The ORR using Nivolumab in the population with advanced non-squamous NSCLC having prior disease progression on a checkpoint inhibitor or patients with non-squamous NSCLC without prior CIT with no/low PD-L1 expression is assumed to be 5% (p_0); thus this rate is considered uninteresting. The target ORR using the investigational agents in combination with Nivolumab in this study is 30% (p_1). Stage 1 of enrollment will include a minimum of 9 evaluable patients in each treatment strata. With exactly 9 evaluable patients at Stage 1, if at least 1 patient has an Objective Response, 8 additional evaluable patients will be enrolled in the treatment stratum, for a total sample size of 17 evaluable patients. If at least 3 Objective Responses are observed in a treatment stratum, further investigation may be warranted. If the true ORR is 5% (null hypothesis), the probability of early termination during the study is 0.63; the Type 1 error is equal to 0.0466 and the power is equal to 0.9045.

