6.2.1.3 Phase 2 CIT-naïve with high PD-L1 expression

The ORR using Nivolumab in the population with non-squamous NSCLC having high PD-L1 expression is assumed to be 27% (p_0); thus this rate is considered uninteresting. The target ORR using the investigational agents in combination with Nivolumab is 50% (p_1).

Stage 1 of enrollment will include approximately 17 evaluable patients. With exactly 17 evaluable patients at Stage 1, if at least 5 patients have Objective Responses, 27 additional evaluable patients will be enrolled, for a total sample size of 44 evaluable patients. If at least 18 Objective Responses are observed, further investigation may be warranted. If the true ORR is 27% (null hypothesis), the probability of early termination during the study is 0.50; the Type 1 error is equal to 0.0303 and the power is equal to 0.9018.

The exact stopping rules for all cohorts will be calculated based on the Predictive Probability Design, once the exact number of patients evaluable at Stage 1 is known. The aim is to get a minimum of 9 evaluable patients at Stage 1 for CIT-experienced and CIT-naïve with no/low PD-L1 expression cohorts and a minimum of 17 evaluable patients at Stage 1 for CIT-naïve with high PD-L1 expression cohort.

The original protocol provided that if results in any strata were of high interest for efficacy, enrollment might be expanded to as many as 100 patients total in each cohort to narrow the 95% CI around the ORR point estimate. Protocol Amendment 3 (v4.0) eliminates enrollment expansion beyond Stage 2 except in the Sitravatinib segment of the study enrolling patients with CIT-experience.

6.2.1.4 Expansion Beyond Phase 2

For the Sitravatinib segment of the study enrolling patients with CIT-experience, expansion of enrollment beyond Stage 2 will be managed as one cohort that includes all patients, regardless of prior clinical benefit during treatment with CIT. Based on preliminary clinical activity results as of June 2018 (described in Section 1.5.3.2.2 of the protocol), enrollment into the combined cohort will expand to as many as 125 patients total, to further evaluate safety and efficacy in this setting.

[figure not shown]
Expansion of Sitravatinib CIT-naïve cohorts beyond Stage 2 of enrollment is not anticipated.

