8.2.1 Objective Response Rate (ORR)

Objective disease response will be categorized in accordance with RECIST v1.1. ORR is defined as the proportion of patients documented to have a confirmed CR or PR. ORR as reported by the investigator will be used in decision making for study expansion (Predictive Probability Design).

Best Overall Response (BOR) is defined as the best response among all overall responses (in the order CR, PR, SD, PD then NE) recorded from the start of study drug until disease progression/recurrence or start of subsequent anti-cancer therapy, whichever comes first. The status of best response of CR or PR must be confirmed by repeat tumor assessment within no less than 4 weeks according to RECIST v1.1. If the status of CR or PR cannot be confirmed by repeat tumor assessment, the BOR of unconfirmed CR and PR will be SD or NE. The status of BOR of SD requires an on-study assessment after at least 42 days from first dose date of treatment.

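### The primary ORR test has power 0.79 and 0.85 at the nominal sizes of the two sitravatinib CIT-naïve strata; the stated power of about 0.90 belongs to the go/no-go rule

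*SAP*

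**What the plan says.** The SAP applies two procedures to the same null ORRs.

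**Go/no-go rule (SAP 6.2.1.2 and 6.2.1.3).** A Predictive Probability Design, with type I error held below 0.05 and power at 0.90 or more.
- CIT-experienced and CIT-naïve with no/low PD-L1: null 5%, target 30%. Nine evaluable patients at Stage 1, continue with at least 1 response, 17 in total, go with at least 3. For this rule "the Type 1 error is equal to 0.0466 and the power is equal to 0.9045".
- CIT-naïve with high PD-L1: null 27%, target 50%. Seventeen at Stage 1, continue with at least 5 responses, 44 in total. "If at least 18 Objective Responses are observed, further investigation may be warranted"; for this rule "the Type 1 error is equal to 0.0303 and the power is equal to 0.9018".

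The rule works on evaluable patients (SAP 10.0: "Tumor responses will be reviewed for the CAE population to make decisions per the Predictive Probability Design"). It may begin from unconfirmed responses (SAP 6.2: "Unconfirmed objective responses recorded in the CRF may be used as the initial basis for expansion of study enrollment").

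**Primary analysis (SAP 11.1.6.1).** "An exact test for single proportion (one-sided $\alpha=0.025$) will be performed to test" the same nulls. On the population, "The primary analysis will be conducted using the FAS with supportive analyses presented using the CAE population", and patients who cannot be assessed count as non-responders. Under SAP 8.2.1, "ORR is defined as the proportion of patients documented to have a confirmed CR or PR".

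SAP 8.5 has each PD-L1 stratum analysed separately. SAP 6.2.1.4 does not anticipate expanding the CIT-naïve cohorts beyond Stage 2, and expands only the combined sitravatinib CIT-experienced cohort, to as many as 125.

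**The concern.** Both type I errors of the go/no-go rule (0.0466 and 0.0303) exceed 0.025, so meeting the rule cannot guarantee that the primary test rejects. A reader who finds power of at least 0.90 in the sample-size section, set against the same nulls that the primary test uses, will assume that the figure carries over to that test. Neither document gives the test's own power, or says which procedure supports a claim that ORR exceeds the null.

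Two things are at stake. A non-significant primary result could be read as if the test had had 90% power. And a stratum with exactly 3/17 or 18/44 responses would be a go while the primary test fails and the reported 95% interval includes the null. If the plan is silent at that point, the more favourable procedure can be chosen after the results are seen.

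The rule and the test can also disagree because of population and response confirmation. This point concerns only the difference in alpha, which remains even when the FAS equals the evaluable set and every response is confirmed.

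**Working it through.** **Inputs.** From SAP 6.2.1.2 and 6.2.1.3: (n1, r1, n, r) = (9, 1, 17, 3) with p0 = 0.05 and p1 = 0.30; and (17, 5, 44, 18) with p0 = 0.27 and p1 = 0.50. From SAP 11.1.6.1: exact test, one-sided alpha 0.025.

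**Formula.** With a Stage 1 stop,

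P(success | p) = Σ over x = r1 to n1 of P[Bin(n1, p) = x] × P[Bin(n − n1, p) ≥ r − x].

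The primary test's critical value is the smallest r with P[Bin(n, p0) ≥ r] ≤ 0.025.

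**Step 1: reproduce the stated figures.**
- 9/17 rule: early termination under the null is 0.95^9 = 0.6302 (stated 0.63); type I error 0.0466; power 0.9045. All match.
- 17/44 rule: early termination is P[Bin(17, 0.27) ≤ 4] = 0.4977 (stated 0.50); type I error 0.0303; power 0.9018. All match.

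**Step 2: critical values of the primary test.**

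| Result | Null | One-sided exact p | 95% Clopper-Pearson | Rejects at 0.025? |
|---|---|---|---|---|
| 3/17 | 5% | 0.0503 | 3.8–43.4% | No |
| 4/17 | 5% | 0.0088 | 6.8–49.9% | Yes |
| 18/44 | 27% | 0.0317 | 26.3–56.8% | No |
| 19/44 | 27% | 0.0150 | 28.3–59.0% | Yes |

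In each stratum the test needs one response more than the go/no-go rule.

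**Step 3: power of the primary test, Stage 1 rule kept.**

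| Stratum | Success | Type I error | Power at target | ORR needed for 0.90 power |
|---|---|---|---|---|
| No/low PD-L1, n = 17 | ≥4 | 0.0086 | 0.790 | 35.6% (target 30%) |
| High PD-L1, n = 44 | ≥19 | 0.0146 | 0.847 | 52.0% (target 50%) |

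Without the Stage 1 stop, power would be 0.798 and 0.854.

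**Step 4: how often the two procedures disagree.** At the target ORR, the chance of continuing and finishing at exactly 3/17 is 0.9045 − 0.7903 = 0.114. For exactly 18/44 it is 0.9018 − 0.8467 = 0.055.

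**Step 5: FAS larger than the evaluable set.** The documents give no non-evaluable rate. Assume 0 to 4 extra FAS patients.
- All extras non-responders: no/low stays at 0.79 (critical value 4 throughout). High is 0.85 at FAS 44–45 (critical value 19) and 0.77 at FAS 46–48 (critical value 20).
- FAS ORR equal to the target: no/low 0.790, 0.825, 0.853, 0.876 and 0.894 at FAS 17 to 21; high 0.847, 0.874, 0.841, 0.869 and 0.892 at FAS 44 to 48.

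Power is below 0.90 at every size in this assumed range.

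**Step 6: CIT-experienced patients.** At n = 125 the test needs 12 responses (p = 0.0231) and has power above 0.999 at 30%. A separately analysed CIT-experienced stratum, taken as single-stage, has power 0.798–0.893 at n = 17–20, 0.914–0.932 at 21–22, 0.864–0.889 at 23–24 and 0.9095 at 25.

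**The case against.** The strongest reply is that nothing in the plan contradicts anything else. The 0.90 constraint is placed on the Predictive Probability Design, the stated figures are right for it, and no document claims 0.90 power for the exact test. Meeting the rule leads only to possible further investigation, and SAP 11.1.6.1 gives the test its own alpha, population and non-responder handling. A go signal without significance at a stricter alpha is an ordinary Phase 2 outcome. It is true that no sentence is false. But a sample size justified by the power of one procedure, when another procedure against the same nulls is primary, leaves the primary test without a stated power and invites the wrong reading.

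The second reply is that 17 and 44 are illustrative. Stage 1 numbers may vary, the stopping rules are recalculated for the actual number, and the 0-to-4 range is an assumption. This also stands. With FAS ORR equal to the target, power passes 0.90 at FAS 22 (0.909) and FAS 51 (0.907). With the extras all non-responders it does not (0.79 at FAS 22; 0.67 at FAS 49–52). Exact-test power also moves unevenly with n: at FAS 46 the critical value is 20 only because 19/46 gives p = 0.02502. So the figures should be labelled nominal. The shortfall at the stated sizes remains.

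The third reply is that the effect is conservative and no decision in the plan depends on rejecting the null. That limits the severity. It does not remove the need to say what the primary test can show.

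Protocol 9.4.1 words the test as two-sided 5%. Run by the minimum-likelihood method, that would give p = 0.042 at 18/44 and reject; 3/17 would still fail at 0.0503. The SAP's one-sided 0.025 excludes that version.

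**Conclusion.** The concern holds and should be fixed. At the nominal sizes, with the Stage 1 rule kept, the FAS equal to the evaluable set and all responses confirmed, the primary test has power 0.79 in no/low PD-L1 and 0.85 in high PD-L1, against the 0.9045 and 0.9018 printed in the sample-size section. The scope is the two sitravatinib CIT-naïve strata, plus the separate CIT-experienced strata only if they stay small. Glesatinib and mocetinostat have no efficacy test (SAP 4.1.1, 4.1.2 and 11.1.6). No false positives are added: the test's type I error (0.0086 and 0.0146) is well under 0.025.

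**What to change.** Keep one-sided 0.025.

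1. In SAP 6.2.1.2 and 6.2.1.3, label 0.9045 and 0.9018 as properties of the go/no-go rule in evaluable patients only.
2. In SAP 11.1.6.1, state the primary test's critical values, power and type I error at the nominal sizes (≥4/17: 0.79 and 0.0086; ≥19/44: 0.85 and 0.0146), to be updated to the actual FAS size.
3. Add one sentence there: meeting the go/no-go rule supports further investigation only, and a claim that ORR exceeds the null rests on the primary test.

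The cost is SAP text and a less favourable stated power for the formal test. There are no extra patients and no change to alpha. SAP 4.0 already provides for a final version before database lock, which is the place to make the change.

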9.4 Efficacy Endpoint Definitions and Analyses

9.4.1 Objective Response Rate

Objective disease response will be categorized in accordance with RECIST v1.1 (Appendix 4). Objective Response Rate (ORR) is defined as the percent of patients documented to have a confirmed Complete Response (CR) or Partial Response (PR). If central review of disease response is undertaken, ORR as reported by the central radiology review laboratory will be used to calculate ORR and the exact 95% confidence intervals (CI). ORR as reported by the Investigator will be used in study expansion decision making (PPD design) and supportive analyses.

Descriptive statistics (frequency and percentage) for ORR, CR, and PR will be presented. The exact 95% CI of these response rates will be calculated. An exact test for single proportion (two-sided α =5%) will be performed to test H₀: ORR \leq 5% against H₁: ORR \geq 5%. Other details will be described in the SAP.

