8.5 Predetermined Covariates and Prognostic Factors

Enrollment into each treatment arm of the CIT-experienced patients will be stratified by prior outcome of treatment with a checkpoint inhibitor (prior clinical benefit, no prior clinical benefit). Each combination of treatment arm and prior clinical benefit stratum, including overall, will be analyzed separately.

Enrollment into each treatment arm of the CIT-naïve patients will be stratified according to the patient's PD-L1 status (No/Low, High). Each combination of treatment arm and PD-L1 status, including overall, will be analyzed separately.

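### The primary-test sentence in SAP 11.1.6.1 places CIT-naïve patients under the 5% null, probably through a slip of *or* for *of*, and protocol 9.4.1 gives one 5% null that conflicts with the 27% null for high PD-L1

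*SAP*

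**What the plan says.** **The SAP test.** SAP 11.1.6.1 specifies an exact single-proportion test at one-sided 0.025. The null of ORR at most 5% is assigned "for CIT-experienced and PD-L1 no/low or CIT naïve for each treatment arm which proceeds to Phase 2". The sentence then assigns a null of ORR at most 27% "for PD-L1 high of CIT naïve".

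**The design rates.** SAP 6.2.1.2 gives 5% as the uninteresting rate for CIT-experienced patients and for CIT-naïve patients with no/low PD-L1. SAP 6.2.1.3 gives a different rate for the other CIT-naïve stratum: nivolumab ORR in patients "having high PD-L1 expression is assumed to be 27" percent. Protocol 9.1.2 has the same two rates.

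**The level of analysis.** SAP 8.5 says of the CIT-naïve patients: "Each combination of treatment arm and PD-L1 status, including overall, will be analyzed separately". SAP 11.1.6 applies section 8.5 to all efficacy analyses. No null rate is written for the overall CIT-naïve group.

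**The protocol test.** Protocol 9.4.1 says "An exact test for single proportion (two-sided α =5%) will be performed", with a null of ORR at most 5% and, as printed, an alternative of at least 5%. It names no cohort and does not mention 27%. It closes with "Other details will be described in the SAP".

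**The change log.** SAP 4.1 lists departures from the protocol. Neither the 27% test nor the move to one-sided 0.025 is among them. Protocol section 9 lets the SAP modify the planned analyses, but says major changes to the primary endpoint's analysis will also appear in a protocol amendment.

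**The concern.** The null rate is the decision threshold of the primary analysis, so a wrong word there matters more than one in background text. Taken at face value, the phrase after *or* covers every CIT-naïve patient. It is also the only wording in the plan that could supply a null for the overall CIT-naïve group that SAP 8.5 asks for. A programmer who follows the text could therefore run a pooled CIT-naïve test against 5%. Most of that group, 44 of 61 at the planned sizes, comes from a stratum in which the plan calls 27% uninteresting. A significant result would then be expected from ordinary nivolumab activity.

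Protocol 9.4.1 adds a second inconsistency. Its one unqualified 5% null does not fit the protocol's own design for high PD-L1. The two printed hypotheses both include 5%. The sidedness also differs from the SAP's.

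**Working it through.** **Inputs** (SAP 6.2.1.2, 6.2.1.3 and 11.1.6.1; protocol 9.1.2 and 9.4.1)
- No/low: null 5%; 9 patients at Stage 1, continue with at least 1 response; 17 in total, success at 3 or more.
- High: null 27%; 17 patients at Stage 1, continue with at least 5 responses; 44 in total, success at 18 or more.
- Test: exact binomial, one-sided 0.025.
- Assumption: the numbers analysed in the FAS equal the planned evaluable numbers.

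**1. The plan's own figures.** Early termination is P(X1 < gate). The rejection probability is the sum, over Stage 1 counts x at or above the gate, of P(X1 = x) × P(X2 ≥ r − x).

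| Stratum | Early termination at null | Type 1 error | Power |
|---|---|---|---|
| No/low, computed | 0.6302 | 0.0466 | 0.9045 |
| No/low, stated | 0.63 | 0.0466 | 0.9045 |
| High, computed | 0.4977 | 0.0303 | 0.9018 |
| High, stated | 0.50 | 0.0303 | 0.9018 |

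All agree. The single-stage errors, 0.0503 and 0.0317, do not match, so the stated figures include the gates.

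**2. Intended SAP reading.** The critical count is the smallest r with P(Bin(n, p0) ≥ r) ≤ 0.025.
- High against 27%, n = 44: the tail is 0.0317 at 18 and 0.0150 at 19, so r = 19. The false-positive rate is 0.0150, or 0.0146 with the gate.
- No/low against 5%, n = 17: the tail is 0.0503 at 3 and 0.0088 at 4, so r = 4. The false-positive rate is 0.0088, or 0.0086 with the gate.

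**3. Literal reading: pooled CIT-naïve against 5%.**
- Average rate when both strata are at their nulls: (17 × 0.05 + 44 × 0.27)/61 = (0.85 + 11.88)/61 = 20.9%.
- Critical count, n = 61: the tail is 0.0321 at 7 and 0.0108 at 8, so r = 8.
- Rejection at full enrolment: P(Bin(17, 0.05) + Bin(44, 0.27) ≥ 8) = 0.961.
- Both strata reach full size in only (1 − 0.6302) × (1 − 0.4977) = 0.3698 × 0.5023 = 18.6% of such trials. With the gates applied, a stopped stratum keeping its Stage 1 patients and the critical count reset to the pooled n, the probability is 0.547.
- The mix matters. With fixed sizes and no gate, 17 + 17 gives 0.470, 9 + 17 gives 0.593 and 9 + 44 gives 0.979.

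**4. Protocol 9.4.1 applied to high PD-L1 at a true 27%.**
- Critical count, n = 44: r = 6 (tail 0.0216). The same count applies under the two-sided 5% exact test.
- Rejection at full enrolment: P(Bin(44, 0.27) ≥ 6) = 0.989.
- With the gate: passing Stage 1 and then rejecting has probability 0.5022. A stopped stratum with exactly 4 of 17 also rejects, since r = 4 at n = 17: 0.7137 − 0.5023 = 0.2114. The total is 0.714.

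**The case against.** The strongest answer is that the SAP sentence explains itself. Its second half assigns 27% to the high stratum of CIT-naïve patients, in parallel wording. If the first half already covered all CIT-naïve patients, high PD-L1 patients would fall under two nulls in one sentence, and naming no/low would be redundant, since PD-L1 strata exist only within the CIT-naïve group. Sections 6.2.1.2 and 6.2.1.3 point the same way. This stands: *of* is almost certainly what was meant.

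Three stronger readings are tempting, and the documents do not support them.
- A reader might infer that the plan tests high PD-L1 against 5%. The SAP does not; it tests that stratum against 27%. Protocol 9.4.1 names no cohort and defers details to the SAP, so extending its 5% null to every cohort is an inference.
- A reader might infer that activity would be declared 96% to 99% of the time under the null. Those figures assume full enrolment. The plan's own early-termination probabilities, 0.63 and 0.50, reduce them to about 0.55 and 0.71. The exact test is also separate from the stated thresholds for further investigation, at least 3 of 17 and 18 of 44.
- A reader might take 20.9% as the plan's null for the pooled group. The plan states no such null; the figure follows from an assumed 17:44 mix.

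It is also fair that SAP 8.5 says analysed, not tested, and that 11.1.6.1 separately provides descriptive rates with Clopper-Pearson intervals. But correcting the slip alone leaves it unsaid whether the overall group is tested, and leaves protocol 9.4.1 at odds with protocol 9.1.2.

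**Conclusion.** The wording of the primary test is defective and should be corrected; the intended tests are sound. With *of* in place of *or*, the false-positive rates are about 1.5% for high PD-L1 against 27% and 0.9% for no/low against 5%.

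Read literally, a pooled CIT-naïve test against 5% would reject with probability about 0.96 at full enrolment or 0.55 with the Stage 1 gates, when neither stratum does better than its uninteresting rate. Protocol 9.4.1 taken alone for high PD-L1 would reject with probability about 0.99 or 0.71 respectively. Even the lowest of these four is over 20 times the nominal 0.025 (0.547/0.025 = 21.9).

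The conclusion rests on true rates of exactly 5% and 27%, on FAS sizes equal to the planned evaluable sizes, and on stopped strata being analysed at their Stage 1 size. The inconsistencies in the text do not depend on these assumptions; the probabilities do.

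**What to change.** - In SAP 11.1.6.1, change *or* to *of*, so that the 5% null covers CIT-experienced patients and the no/low PD-L1 stratum of CIT-naïve patients only.
- In SAP 11.1.6.1 or 8.5, state that overall CIT-naïve ORR is estimated with its exact confidence interval and not tested.
- In protocol 9.4.1, give both cohort nulls (5% and 27%), make the alternative strictly greater, and use the SAP's one-sided 0.025.
- In SAP 4.1, list the cohort-specific null and the change of sidedness.

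The cost is four small text edits, one of them to the protocol, with no extra data or patients. SAP 4.0 already provides for a final SAP version before database lock, which is a natural point for the SAP edits.
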